13.3 Ethics

This study is to be conducted according to the following considerations, which represent good and sound research practice:

- US Code of Federal Regulations (CFR) governing clinical study conduct and ethical principles that have their origin in the Declaration of Helsinki
 - Title 21 Part 50 – Protection of Human Subjects
www.access.gpo.gov/nara/cfr/waisidx_02/21cfr50_02.html
 - Title 21 Part 54 – Financial Disclosure by Clinical Investigators
www.access.gpo.gov/nara/cfr/waisidx_02/21cfr54_02.html
 - Title 21 Part 56 – Institutional Review Boards
www.access.gpo.gov/nara/cfr/waisidx_02/21cfr56_02.html
 - Title 21 Part 312 – Investigational New Drug Application
www.access.gpo.gov/nara/cfr/waisidx_02/21cfr312_02.html

CONFIDENTIAL

This document is confidential. Do not disclose or use except as authorized.

- State laws
- DF/HCC research policies and procedures
<http://www.dfhcc.harvard.edu/clinical-research-support/clinical-research-unit-cru/policies-and-procedures/>

It is understood that deviations from the protocol should be avoided, except when necessary to eliminate an immediate hazard to a research participant. In such case, the deviation must be reported to the IRB according to the local reporting policy.

13.4 Study Documentation

The investigator must prepare and maintain adequate and accurate case histories designed to record all observations and other data pertinent to the study for each research participant. This information enables the study to be fully documented and the study data to be subsequently verified.

Original source documents supporting entries in the case report forms include but are not limited to hospital records, clinical charts, laboratory and pharmacy records, recorded data from automated instruments, microfiches, photographic negatives, microfilm or magnetic media, and/or x-rays.

13.5 Records Retention

All study-related documents must be retained for the maximum period required by applicable federal regulations and guidelines or institutional policies.

14. STATISTICAL CONSIDERATIONS

14.1 Background Data for Sample Size Justification

This study will enter patients who have either relapsed within 1 year of completing adjuvant endocrine therapy and/or who have progressed through at least one line of metastatic endocrine therapy. Patients who have previously received either fulvestrant or an HSP90 inhibitor are excluded. There is no limit on the number of prior lines of metastatic endocrine therapy. Up to one line of chemotherapy for metastatic disease is allowed.

The EFECT trial entered patients with ER-positive metastatic breast cancer who have progressed on a non-steroidal aromatase inhibitor.⁴ Patients were randomized to receive fulvestrant versus exemestane. Approximately 60% of patients had received 2 or more prior lines of hormonal therapy (adjuvant + metastatic). Median time to progression was 3.7 months in both groups. Overall response rate was similar (7.4% v 6.7%; p=0.74). Clinical benefit rate (CR + PR + SD \geq 6 months) was also similar (32.2% v 31.5%; p=0.85). The proportion of patients who came off study for a reason other than progression was not specifically reported in this study. However, at

CONFIDENTIAL

This document is confidential. Do not disclose or use except as authorized.

the time of study reporting, 82% of the fulvestrant group and 87% of the exemestane group had experienced a defined progression event.

CALGB 40302 entered patients with ER-positive metastatic breast cancer who had previously been treated with an aromatase inhibitor, up to 2 lines of endocrine therapy for metastatic disease, and up to 1 prior line of metastatic chemotherapy.⁵ Patients were randomized to fulvestrant with or without lapatinib. The study was terminated early for futility after the third planned interim analysis. Approximately half of patients had received prior tamoxifen; 28% of patients had bone-only disease. Median progression-free survival in the fulvestrant alone arm was 4.0 months.

14.2 Primary Clinical Objective and Sample Size Justification

Progression Free Survival (PFS): Progression-free survival is defined as time from randomization until time of progression or death, whichever comes first. Patients who stop protocol therapy (either fulvestrant or ganetespib or both) for a reason other than progression or death should continue to be followed for progression per Study Calendar D. For subjects who do not progress or die, PFS will be censored at the time of last tumor evaluation before initiation of alternative anti-cancer treatment.

Analysis Population: All randomized patients will be included in the analysis of PFS. The analysis will be conducted based on intention to treat (ITT). However, data imputation will not be used for PFS. So patients with no follow-up at all will be censored for PFS at the date of randomization.

If the interim safety analysis indicates that the starting dose of ganetespib should be decreased to 175 mg/m², these patients will be combined with the patients who received a starting dose of 200 mg/m² in the ITT analysis. That is, all randomized patients will be included in the ITT analysis, regardless of starting dose and regardless of whether or not treatment was stopped early for any reason.

Power Calculation

The primary objective of this randomized, phase II study is to investigate whether ganetespib, when given in combination with fulvestrant, improves progression-free survival (PFS) compared to fulvestrant alone, in patients with ER-positive, metastatic breast cancer. This study will have a 1:2 randomization ratio: 24 patients will be randomized to Arm A (fulvestrant alone) and 47 patients will be randomized to Arm B (fulvestrant + ganetespib), for a total of 71 randomized patients. The expected accrual rate is ~3.5 to 4.5 patients per month over a period of ~20 months.

As this is an exploratory phase II study, no interim efficacy analyses are planned and there are no early stopping rules for efficacy (or lack of efficacy) in this study.

The primary comparison will be a one-sided log rank test of whether PFS is longer in patients randomized to Arm B (fulvestrant + ganetespib) than those randomized to Arm A (fulvestrant).

CONFIDENTIAL

This document is confidential. Do not disclose or use except as authorized.

A maximum of 20% of patients (n=14) on this trial may be entered on the strata for patients with non-measurable but evaluable disease (a category which includes but is not limited to patients with bone-only disease). The primary comparison will not be stratified by type of disease (measurable or non-measurable) because the stratification is being used as a mechanism to limit the number of patients with only non-measurable disease.

Based upon data from the EFECT trial, we further assume that up to 11 patients (15%) may be censored for PFS because of being lost to follow-up or receiving non-protocol anti-cancer therapy before they have progressed or died, and that this probability is not different in the two arms.⁴ To be conservative, we assume that this censoring occurs very close to the time that the patient enters the study, so the effective total sample size will be 60, with 20 patients randomized to fulvestrant alone and 40 patients randomized to fulvestrant + ganetespib.

Assuming that PFS has an exponential distribution, and that the true median PFS on Arm A (fulvestrant alone) is 4.0 months, and that accrual takes 20 months (3.5 patients per month), there will be 80% power to detect a prolongation of true median PFS to 8.0 months in Arm B (fulvestrant + ganetespib), using a one-sided 0.05 log-rank test if the patients are followed for 20 months after accrual ends (so, 40 months after accrual starts). If accrual takes only 15 months (4.5 patients per month) and follow up extends to 22 months after accrual ends, there will also be 80% power. If the true median PFS on the single agent arm is longer than 4 months, the power calculations will still be correct as long as the ratio of medians remains the same (e.g. true medians of 5 and 10 months will have the same power as the true medians of 4 and 8 months, provided that the patients are followed long enough to have the same number of expected PFS events, which is 57).

If more than 2 patients of the first 10 have confirmed DLTs, the study will then re-open at Dose Level -1. If more than 2 of the first 10 patients randomized to arm B at Dose Level -1, study accrual will be temporarily suspended and the events will be adjudicated. If the events are confirmed by the Principal Investigator to be true DLTs, the study will close permanently to new accrual. Results will be shared with patients already enrolled on study, but they will be allowed to continue on therapy.

With this design, the probability of stopping accrual at or before 10 patients at Dose Level -1 is 0.18 if the true DLT rate is 15%, 0.68 if the true DLT rate is 20%, and 0.90 if the true DLT rate is 45%.

14.4 Analysis of Secondary Clinical Endpoints

Safety and toxicity: All patients who received at least one dose of protocol therapy (fulvestrant, ganetespib, or both) will be included in the safety/toxicity analysis. Toxicity will be graded according to NCI CTCAE, Version 4.0. The proportion of patients who experience each type and grade of toxicity will be presented in tabular form. Toxicity will be described separately in Arm A (pre-crossover), Arm C (post-crossover), and Arm B.

Objective Response Rate: All patients with measurable disease at baseline will be included in the analysis of response rate. Response will be assessed using RECIST 1.1, as described in Section 10. The response rate will be calculated separately in Arms A, B, and C. Response rates in Arm A and Arm B will be compared using a one-sided Fisher exact test. An intent to treat analysis will be used, so all patients randomized in the measurable disease stratum will be used in the

analysis; patients with no follow-up response evaluation will be assumed to be non-responders. Assuming that 57 patients are entered in the measurable disease stratum, there will be 81% power to decide that the ganetespib arm has a better response rate if the true response rates on the two arms are as different as 36% and 5%, or 44% and 10%.

Clinical benefit rate: Clinical benefit will be defined as CR + PR + SD \geq 6 months. All patients will be included in the analysis of clinical benefit. CBR will be calculated separately in Arms A and B, and compared using a one-sided Fisher exact test. All patients randomized on study will be used in this analysis, and patients with no follow-up response evaluation will be assumed not to have clinical benefit. With 71 patients randomized, there will be 80% power to decide that the ganetespib arm has a better clinical benefit rate if the true benefit rates on the two arms are as different as 63% and 30%, or 73% and 40%.

Overall survival: Overall survival is defined as duration of time from randomization to death due to any cause, or censored on the date last known alive. All randomized patients will be included in the analysis of OS. OS will be estimated separately in Arm A and Arm B. OS will be analyzed at the same time as the final analysis of PFS, although it is acknowledged that the percent of survival censoring at that time will be larger than the percent of PFS censoring, and this will limit the power to detect survival differences between the arms.

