2.5 Summary

This is a randomized phase II trial evaluating fulvestrant with or without ganetespib, a potent, novel HSP90 inhibitor. The primary clinical objective is progression-free survival. We hypothesize that ganetespib will augment the efficacy of fulvestrant and be associated with an improvement in progression-free survival.

Secondary clinical endpoints include objective response rate (among patients with measurable disease at baseline), safety/tolerability, clinical benefit rate (CR + PR + SD \geq 6 months), and overall survival.

The correlative objectives of this study include evaluation of the relationship between HSF1 and clinical outcome, alterations in heat-shock network function, ER expression and transcriptional activity, and alterations in other relevant downstream targets. Patients who enroll on this trial will also be approached regarding an ¹⁸FES-PET companion study (which will be written as an entirely separate, IRB-approved protocol) when it is available.

CONFIDENTIAL

This document is confidential. Do not disclose or use except as authorized.

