6. EXPECTED TOXICITIES AND DOSING DELAYS/DOSE MODIFICATIONS

Dose delays and modifications will be made using the following recommendations. Toxicity assessments will be done using the CTEP Active Version of the NCI Common Terminology Criteria for Adverse Events (CTCAE) v 4.0 which is identified and located on the CTEP website at: http://ctep.cancer.gov/protocolDevelopment/electronic_applications/ctc.htm.

If possible, symptoms should be managed symptomatically. In the case of toxicity, appropriate medical treatment should be used (including anti-emetics, anti-diarrheals, etc.).

All adverse events experienced by participants will be collected from the time of the first dose of study treatment, through the study and until the final study visit. Participants continuing to experience toxicity at the off study visit may be contacted for additional assessments until the toxicity has resolved or is deemed irreversible.

CONFIDENTIAL

This document is confidential. Do not disclose or use except as authorized.

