14.6 Reporting and Exclusions

14.6.1 Evaluation of toxicity.

All participants will be evaluable for toxicity if they received any protocol therapy.

14.6.2 Evaluation of response.

All participants randomized on the study who have RECIST measurable disease must be assessed for response to treatment, even if there are major protocol treatment deviations, or they receive no treatment, or if they are ineligible. Participants who have no follow-up tumor evaluations, who die or receive non-protocol anticancer therapy before a response is noted, or who have unknown or not-assessable response will count as non-responders.

CONFIDENTIAL

This document is confidential. Do not disclose or use except as authorized.

14.6.3 Evaluation of progression-free survival.

All participants randomized on the study must be assessed for PFS, even if there are major protocol treatment deviations, or they receive no treatment, or if they are ineligible. However, there will be no imputation of any missing progression-free survival times.

14.6.4 Analyses of Subsets of Patients.

For all endpoints except toxicity, the primary analysis will be based on all randomized patients (and the primary analysis of toxicity will be based on all patients who receive at least one dose of one of the study agents). However, in addition to the primary analysis, analysis of subsets of patients may be done (e.g., analysis restricted to eligible patients or to patients who receive at least one cycle of therapy). However, these analyses of subsets will be considered exploratory and will not serve as the basis for drawing conclusions about treatment efficacy.

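### Toxicity is summarised only as the proportion of patients ever affected, so if ganetespib lengthens PFS, Arm B's longer observation alone can raise its counts of unrelated events

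*Combined protocol and SAP*

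**What the plan says.** Section 14.4 (safety and toxicity) states: "The proportion of patients who experience each type and grade of toxicity will be presented in tabular form". It continues: "Toxicity will be described separately in Arm A (pre-crossover), Arm C (post-crossover), and Arm B". Section 14.6.1 adds only the population: "All participants will be evaluable for toxicity if they received any protocol therapy". Neither section names person-time, a common time window, a time-to-first-event method or a summary of treatment duration.

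Other sections fix how long each patient is at risk of being counted:

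- Section 5 continues treatment until progression unless toxicity, withdrawal or death comes first.
- Section 6 says "All adverse events experienced by participants will be collected from the time of the first dose of study treatment", and carries collection on to the final study visit.
- Study Calendar D (Section 9.4) keeps AE evaluation every 4 weeks for patients who leave assigned therapy without progression.
- Section 11.1.1 counts an AE whether or not it is thought related to the study.

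The design assumption on PFS is in Section 14.2: "the true median PFS on Arm A (fulvestrant alone) is 4.0 months", and "there will be 80% power to detect a prolongation of true median PFS to 8.0 months in Arm B". Section 2.5 states the direction: "We hypothesize that ganetespib will augment the efficacy of fulvestrant and be associated with an improvement in progression-free survival".

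**The concern.** An ever/never proportion grows with time at risk. Here time at risk is tied to the primary endpoint, and Arm A's pre-crossover column closes at progression for patients who cross over. If ganetespib delays progression, Arm B patients have longer to experience infections, pain, fatigue or laboratory events that would have occurred anyway.

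At stake is how the safety tables are read. Section 14.3 notes that there are no phase I data on the combination, so the randomised fulvestrant arm is the plan's only direct reference for the toxicity of adding ganetespib. The interim rule in Section 14.3 does not fill this gap, since it covers only cycle 1 dose-limiting toxicities in the first 10 treated Arm B patients and leaves out Arm A.

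**Working it through.** **Inputs from Section 14.2.** Exponential PFS; medians 4.0 and 8.0 months; 20 v 40 effective patients; one-sided 0.05 log-rank test; 57 expected events; 80% power.

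**The plan's own figure.** Power is Φ(√(57 × 1/3 × 2/3) × ln 2 − 1.645) = Φ(3.559 × 0.693 − 1.645) = Φ(0.82) = 79.4%. With uniform accrual over 20 months and 20 months' further follow-up, expected events are 19.8 in Arm A plus 36.6 in Arm B, or 56.5 before rounding the parts. A log-rank simulation (20,000 runs) gives 80.2%. The stated 80% and 57 are reproduced, so the twofold PFS ratio is what the design rests on.

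**Time at risk.** Progression hazards are h_A = ln 2/4 = 0.1733 and h_B = ln 2/8 = 0.0866 per month. Mean times to progression are 1/h = 5.8 and 11.5 months, a ratio of 2.0.

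**Crude incidence of an unrelated event.** Assume a constant rate r per month, the same in both arms. The documents give no such rate, so a range is shown. Then P(ever affected) = r/(r + h).

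| r per month | Arm A | Arm B | Gap (points) |
|---|---|---|---|
| 0.01 | 0.01/0.1833 = 5.5% | 0.01/0.0966 = 10.3% | 4.9 |
| 0.05 | 0.05/0.2233 = 22.4% | 0.05/0.1366 = 36.6% | 14.2 |
| 0.10 | 0.10/0.2733 = 36.6% | 0.10/0.1866 = 53.6% | 17.0 |

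**First 56 days.** With τ = 56/30.4 = 1.842 months, P = r/(r + h) × (1 − exp(−(r + h)τ)).

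- r = 0.05: Arm A 0.22393 × 0.33722 = 0.0755 (7.6%); Arm B 0.36592 × 0.22253 = 0.0814 (8.1%).
- r = 0.10: Arm A 0.36592 × 0.39554 = 0.1447 (14.5%); Arm B 0.53578 × 0.29094 = 0.1559 (15.6%).

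**First events per patient-month.** Expected first events per patient are r/(r + h). Expected time to first event or end of observation is 1/(r + h). The ratio is r in both arms, so under a constant hazard the gap disappears.

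**Sensitivity at r = 0.05.**

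- Arm B median only 6 months (h = ln 2/6 = 0.1155): 22.4% v 0.05/0.1655 = 30.2%.
- Equal medians: no gap.
- One extra month of AE collection after progression in both arms, P = 1 − h/(r + h) × exp(−r): 1 − 0.7761 × 0.9512 = 26.2% v 1 − 0.6341 × 0.9512 = 39.7%.

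The crude formula follows everyone to progression. At the planned analysis about 3.4 of 40 effective Arm B patients (40 − 36.6) would not yet have progressed, so the crude gaps are slightly overstated.

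**The case against.** **Safety is not a comparative objective.** Section 1.3 sets out to assess the safety of the combination, while the other three secondary objectives are to be described and compared. Section 14.4 plans no between-arm test of toxicity. This stands: no planned inference is invalid. The tables will still show the randomised arms separately, and readers will compare them.

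**Misreading is not inevitable.** A reader might infer that the plan expects doubled exposure and that unrelated events will therefore pass as ganetespib toxicity. The documents do not support that. The 4 v 8 months is the alternative used for power plus a stated hypothesis, and five-level attribution is recorded for each event (Section 11.1.4). Section 14.4 does not commit to using attribution in the tables, so the most that can be said is that such events could appear more often in Arm B.

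**Size.** Rarer events give smaller gaps. Section 6.1.2 puts the most common Grade 3 or higher fulvestrant toxicities at 2%. With 24 and 47 patients, a 14.2-point gap has a standard error of √(0.224 × 0.776/24 + 0.366 × 0.634/47) = 11.0 points, so it is only about 1.3 standard errors. The main ganetespib toxicity, diarrhea, typically begins 2 to 3 hours after dosing (Section 5.5) and would mostly show up early. All of this stands and limits the point to events that accrue over time.

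**Laboratory detection.** It is tempting to add that extra Arm B blood draws inflate laboratory toxicity, and to compare arms on shared Day 1 draws. Section 11.1.1 counts an abnormal value as an AE only if it causes signs or symptoms or needs treatment or further tests, so silent mid-cycle values do not count. From cycle 2, each Day 1 draw follows about two weeks without ganetespib, so a Day 1 comparison would tend to miss transient toxicity. The difference in schedule is real from cycle 1 (Calendars A and B) and should be noted, but it does not justify that restriction.

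**The alternatives have flaws.** A 56-day window omits later toxicity and keeps one unequal AE visit (Cycle 1 Day 8, Arm B only). A patient-month rate dilutes front-loaded events when observation is longer. Neither should replace the crude table.

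**Conclusion.** The point holds as a limitation of the planned summary. The only toxicity measure in Section 14.4 depends on observation time, and under the design alternative that time is about twice as long in Arm B as in Arm A pre-crossover. For unrelated events that accrue steadily, the artificial excess runs from about 5 points (r = 0.01) to 17 points (r = 0.10).

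This rests on constant background rates that are assumed, exponential PFS with medians of 4 and 8 months, and AE observation that ends at progression. Ganetespib itself may stop earlier, for toxicity or by choice after at least 6 cycles (Section 5.7). Patients then remain on study with AEs still collected, so the ratio applies to AE observation and not necessarily to ganetespib exposure.

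The documents do not support a claim that the crude table is wrong in itself, or that adjusting for exposure would make Arm C comparable: Arm C is non-randomised treatment after progression. The primary endpoint is unaffected.

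**What to change.** In Section 14.4, keep the crude table. Add, for Arm A (pre-crossover) and Arm B, for all-grade and for Grade 3 or higher events:

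- (a) duration of treatment and of AE observation;
- (b) incidence in the first two cycles (56 days);
- (c) first events per patient-month of AE observation.

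State that any A v B difference in the crude table is to be interpreted alongside (a) to (c). Show the same measures descriptively for Arm C, without treating it as comparable. Beside the laboratory toxicity table, note that on-treatment draws are on Days 1, 8 and 15 in Arm B and on Day 1 only in Arm A.

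The cost is a little more analysis work. AE dates are already required (Section 11.9), and treatment and AE forms are submitted each cycle (Section 12.1.2), so no new data are needed. The early window misses late toxicity and the rate assumes a roughly constant hazard, which is why all the measures should be shown together.

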5.1.4 Cycle 1, Day 8 (Arm B only)

- Clinic visit
- Record concomitant medications
- Vital signs (heart rate, blood pressure, and respiratory rate)
- Physical examination
- Weight
- ECOG performance status
- Record AEs (using CTCAE v4 grading criteria)
- Laboratory assessments
 - Hematology: hemoglobin, hematocrit, white blood cell count with differential, platelet count
 - Serum chemistry: sodium, potassium, chloride, bicarbonate, blood urea nitrogen, creatinine, glucose (random), total bilirubin, alkaline phosphatase, ALT, AST, albumin
 - Serum calcium, magnesium, phosphorus
- Ganetespib administration via silicone VADS

5.1.5 Cycle 1, Day 15

- Clinic visit
- Record concomitant medications

CONFIDENTIAL

This document is confidential. Do not disclose or use except as authorized.

- Vital signs (heart rate, blood pressure, and respiratory rate)
- Physical examination
- Weight (Arm B only)
- ECOG performance status
- Record AEs (using CTCAE v4grading criteria)
- Laboratory assessments (Arm B only)
 - Hematology: hemoglobin, hematocrit, white blood cell count with differential, platelet count
 - Serum chemistry: sodium, potassium, chloride, bicarbonate, blood urea nitrogen, creatinine, glucose (random), total bilirubin, alkaline phosphatase, ALT, AST, albumin
 - Serum calcium, magnesium, phosphorus
- Fulvestrant administration via intramuscular injection
- Ganetespib administration via silicone VADS (Arm B only)

5.1.6 Cycle 2, Day 1

- Clinic visit
- Record concomitant medications
- Vital signs (heart rate, blood pressure, and respiratory rate)
- Physical examination
- Weight (Arm B only)
- ECOG performance status
- Record AEs (using CTCAE v4.0 grading criteria)
- Laboratory assessments
 - Hematology: hemoglobin, hematocrit, white blood cell count with differential, platelet count
 - Serum chemistry: sodium, potassium, chloride, bicarbonate, blood urea nitrogen, creatinine, glucose (random), total bilirubin, alkaline phosphatase, ALT, AST, albumin
 - Serum calcium, magnesium, phosphorus
- 12-lead ECG (Arms B and C only). If pre-dose QTc >470 ms a repeat ECG is required approximately 24 hours after the Ganetespib dose.
- Fulvestrant administration via intramuscular injection
- Ganetespib administration via silicone only VADS (Arm B only)

5.1.7 Cycle 2, Day 8

- Research blood draw for PBMC and CTC analysis. See Section 9.5 and Appendix C for details.

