5.1.9 Cycle 2, Days 8 and 15 (Arm B only)

- Vital signs (heart rate, blood pressure, and respiratory rate)
- Weight
- Laboratory assessments
 - Hematology: hemoglobin, hematocrit, white blood cell count with differential, platelet count
 - Serum chemistry: sodium, potassium, chloride, bicarbonate, blood urea nitrogen, creatinine, glucose (random), total bilirubin, alkaline phosphatase, ALT, AST, albumin
 - Serum calcium, magnesium, phosphorus
- Ganetespib administration via silicone VADS

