5.1.10 Cycle 3 Day 1, and Day 1 of Subsequent Cycles

- Clinic visit
- Record concomitant medications
- Vital signs (heart rate, blood pressure, and respiratory rate)
- Physical examination
- Weight (Arm B only)
- ECOG performance status
- Record AEs (using CTCAE v4 grading criteria)
- Laboratory assessments
 - Hematology: hemoglobin, hematocrit, white blood cell count with differential, platelet count

CONFIDENTIAL

This document is confidential. Do not disclose or use except as authorized.

- Serum chemistry: sodium, potassium, chloride, bicarbonate, blood urea nitrogen, creatinine, glucose (random), total bilirubin, alkaline phosphatase, ALT, AST, albumin
- Serum calcium, magnesium, phosphorus
- CEA, CA27-29, if elevated at baseline. In patients with elevated markers at baseline, tumor markers should subsequently be drawn once every 2 cycles.
- 12-lead ECG (Arms B and C only). If pre-dose QTc >470 ms a repeat ECG is required approximately 24 hours after the Ganetespib dose. See section 5.6 for additional ECG requirements for patient at moderate to high risk of torsades de pointes.
- Radiologic imaging studies to evaluate tumor status. Contrast computed tomography (CT) (or without contrast if contraindicated) of chest and abdomen is preferred. Magnetic resonance imaging (MRI) of chest and abdomen is an acceptable alternative. Note: PET-CT scans are *not allowed* per protocol for primary assessment of response. PET-CT scans may be done according to clinical judgment to supplement CT or MRI scans in cases where results of the PET-CT may clarify or resolve a clinical question.
- Measurements of palpable/visible lesions, if used as a target lesion (for example, chest wall nodule)
- Follow-up imaging and measurements should be done every 2 cycles (8 weeks) and every 2-4 cycles (8-16 weeks) for patients who have been on study for >1 year. Imaging can be done +/- 1 week from targeted date but before start of the subsequent cycle.

5.1.11 Days 8 and 15 of Cycle 3 and Subsequent Cycles (Arm B only)

- Vital signs (heart rate, blood pressure, and respiratory rate)
- Weight
- Laboratory assessments
 - Hematology: hemoglobin, hematocrit, white blood cell count with differential, platelet count
 - Serum chemistry: sodium, potassium, chloride, bicarbonate, blood urea nitrogen, creatinine, glucose (random), total bilirubin, alkaline phosphatase, ALT, AST, albumin
 - Serum calcium, magnesium, phosphorus
- Ganetespib administration via silicone VADS

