- e. All patients should have baseline tumor marker measurement and tumor marker measurement at time of cross-over. Tumor markers are required at other timepoints only when elevated at baseline.
- f. EKG required at time of progression only for patients intending to cross over to Arm C.
- g. Baseline symptoms should be documented using the CTCAE v 4.0 grading scale. Adverse events should be documented on day 1 of each cycle, at each clinic visit, and at time of progression, using the CTCAE v 4.0 grading scale.
- h. Radiologic imaging studies to evaluate tumor status should be done every 2 cycles +/- 7 days. However, patients who have been on-study for >1 year are permitted to have tumor imaging performed every 2-4 cycles. Contrast computed tomography (CT) (or without contrast if contraindicated) of chest and abdomen is preferred. Magnetic resonance imaging (MRI) of chest and abdomen is an acceptable alternative. Note: PET-CT scans are not allowed per protocol for primary assessment of response. PET-CT scans may be done according to clinical judgment to supplement CT or MRI scans in cases where results of the PET-CT may clarify or resolve a clinical question. If palpable/visible lesions (e.g. chest wall nodule, etc) are being used as target lesions, measurements and photographs should be taken as well.

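### The Section 14.4 toxicity table sets Arm A beside Arm B, although short-lived laboratory, ECG and interim-weight toxicities are looked for much less often in Arm A

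*Combined protocol and SAP*

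**What the plan says.** Section 14.4 sets the denominator: "All patients who received at least one dose of protocol therapy (fulvestrant, ganetespib, or both) will be included in the safety/toxicity analysis". It sets the summary: "The proportion of patients who experience each type and grade of toxicity will be presented in tabular form". It sets the layout: "Toxicity will be described separately in Arm A (pre-crossover), Arm C (post-crossover), and Arm B". It names no test for toxicity, no allowance for how often a parameter is measured, and no rule for a parameter that was not measured. Section 14.2 gives the arm sizes: "24 patients will be randomized to Arm A (fulvestrant alone) and 47 patients will be randomized to Arm B".

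The measurement schedules differ by arm.

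- **Laboratory.** The Cycle 1 Day 8 visit exists only in Arm B. The Cycle 1 Day 15 list in Section 5.1.5 carries the line "Laboratory assessments (Arm B only". The section for the later Cycle 2 visits is headed "5.1.9 Cycle 2, Days 8 and 15 (Arm B only", and Section 5.1.11 extends the same restriction to Cycle 3 onward. Calendar A has counts and chemistry on Day 1 of each cycle and at progression or off-treatment.
- **ECG.** From Cycle 3, Section 5.1.10 lists "12-lead ECG (Arms B and C only"; the Cycle 2 Day 1 list has the same restriction. Calendar B adds Cycle 1 Day 2, and a 24-hour repeat if the pre-dose QTc exceeds 470 ms. Calendar A has a pre-study ECG and then, in footnote f: "EKG required at time of progression only for patients intending to cross over to Arm C". Section 5.1.2 lists a Cycle 1 Day 1 ECG without restricting it by arm; Calendar A does not show it.
- **Weight.** Arm B is weighed at each ganetespib visit. Calendar A has weight at Cycle 1 Day 1 and at progression or off-treatment.

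Once ganetespib is stopped, Arm B patients move to Calendar D: counts and chemistry every 8 weeks, with no ECG or weight row.

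**The concern.** A test-detected toxicity can enter the table only if the test is done while the abnormality is present. Counting every treated patient in the denominator treats not looking as not occurring, and the two arms are looked at with different intensity.

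Safety of the combination is a secondary objective (Section 1.3). There are no phase I data for the combination (Sections 5.3 and 14.3), and Arm A before crossover is the only randomized comparator. The parameters affected matter for ganetespib: Section 6.1.1 lists raised AST, ALT and alkaline phosphatase, anemia and hypokalemia among its common events, and Section 2.1 says the QT effect is not yet fully characterized. A QTc entry near 0% out of all treated Arm A patients would look like a control rate when it was hardly measured.

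**Working it through.** The plan states no expected rate, power or error rate for the toxicity table, so there is no figure of its own to reproduce. The check counts scheduled assessments and asks what they would detect if both arms had the same true background rate and equal follow-up.

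**Step 1. Scheduled measurements, from Calendars A and B**

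| Parameter | Arm A | Arm B on ganetespib |
|---|---|---|
| Counts and chemistry per 28-day cycle | 1 (Day 1) | 3 (Days 1, 8, 15) |
| ECG after baseline | at progression, only before crossover | Cycle 1 Day 2, then before each later Day 1 dose |
| Weight after Cycle 1 Day 1 | at progression or off-treatment | each ganetespib visit |

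**Step 2. One laboratory episode of d days, starting at random in a cycle.** Arm A has one 28-day gap between draws. Arm B has gaps of 7, 7 and 14 days. The probability that a scheduled draw falls inside the episode is

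- Arm A: min(d, 28)/28
- Arm B: [2·min(d, 7) + min(d, 14)]/28

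| d (days) | Arm A | Arm B | Ratio |
|---|---|---|---|
| 7 | 7/28 = 0.25 | 21/28 = 0.75 | 3.0 |
| 10 | 10/28 = 0.36 | 24/28 = 0.86 | 2.4 |
| 14 | 14/28 = 0.50 | 28/28 = 1.00 | 2.0 |
| 21 | 21/28 = 0.75 | 1.00 | 1.33 |
| 28 | 1.00 | 1.00 | 1.0 |

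Below 7 days the ratio stays at 3.0.

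**Step 3. Proportion of patients listed after 4 cycles in each arm.** The documents give no background rate, so the rates below are assumptions shown over a range. With independent draws and probability p of an abnormal result at each draw, the proportion is 1 − (1 − p)^k, with k = 4 draws in Arm A and 12 in Arm B.

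| p per draw | Arm A | Arm B | Ratio |
|---|---|---|---|
| 1% | 3.9% (0.9 of 24) | 11.4% (5.3 of 47) | 2.9 |
| 2% | 7.8% (1.9 of 24) | 21.5% (10.1 of 47) | 2.8 |
| 5% | 18.5% (4.5 of 24) | 46.0% (21.6 of 47) | 2.5 |

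The episode model gives a similar picture. At an assumed 0.1 seven-day episodes per cycle, Arm A lists 1 − exp(−0.1 × 4 × 0.25) = 9.5% of patients and Arm B 1 − exp(−0.1 × 4 × 0.75) = 25.9%.

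**Step 4. ECG and weight.** No rate is needed here. A QTc change that came and went before progression has no scheduled Arm A ECG that could show it. A weight change that recovered before the off-treatment visit has no scheduled Arm A weight that could show it.

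**Step 5. Day 1 draws only.** With one common draw per cycle over the same number of cycles, the laboratory detection ratio is 1.0 by construction.

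**The case against.** The strongest objection is Section 11.1.1: an abnormal test is an adverse event only if it causes signs or symptoms, is treated, or leads to further testing. Step 3 counts every silent abnormality that meets a draw, and many would fail this rule. That stands, and it makes the ratios upper bounds. It does not bring them to 1, because the filter also differs by arm: the repeat ECG for QTc above 470 ms is triggered only on ganetespib, and the advice to correct electrolytes in Section 5.6.2 belongs to the ganetespib QT guidance. Appendix G, Section 4.0 names all laboratory tests as safety parameters, so whether silent graded values are tabulated is unsettled.

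Other points also stand:

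- No test of toxicity between arms is planned. A reader might infer that a planned safety inference is biased; the documents contain none.
- A reader might infer that all background events will be credited to ganetespib. Section 11.1.4 provides five-level attribution, and the common symptomatic toxicities (diarrhea, nausea, fatigue) do not depend on a test. From Cycle 2 the scheduled adverse event evaluation is on Day 1 in both arms.
- A reader might infer that Arm A has no ECG or weight after baseline. It has an off-treatment weight, and patients crossing over have an ECG before their first ganetespib dose.
- Three draws per cycle holds only on ganetespib. On Calendar D an Arm B patient has fewer laboratory draws than an Arm A patient still on Calendar A, so the imbalance reverses for that time.
- For laboratory tests the cause is draw frequency. Restricting the denominator to patients with a post-baseline value would change little, since Arm A is tested every cycle.

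Denser testing on an investigational drug is deliberate and is not criticized here. The point concerns how the results are tabulated.

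**Conclusion.** The point holds in a limited form. While Arm B is on ganetespib, short-lived toxicities found only by laboratory test, ECG or interim weight are under-detected in Arm A relative to Arm B. For laboratory abnormalities the detection ratio is at most 3.0 for episodes of 7 days or less, 2.0 at 14 days, 1.33 at 21 days and 1.0 at 28 days or more.

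The 1 v 3 draw count comes from the documents. The patient percentages rest on assumed background rates, episode lengths and equal follow-up of 4 cycles, and on every detected abnormality being counted, so the text does not support a claim that the table will show a threefold excess. Unequal time on treatment is a separate source of imbalance that these figures leave out. The harm is to the reading of a descriptive safety table.

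**What to change.** In Section 14.4:

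1. Keep the full all-assessment tables by arm.
2. Add a supplementary Arm A v Arm B table of laboratory toxicity present at the scheduled Day 1 draws, limited to time on Calendars A and B and to a common number of cycles.
3. Report ECG and weight toxicities over patients with a post-baseline, pre-crossover measurement, giving that number and its timing. Mark QTc and interim weight in Arm A as not scheduled during treatment, in place of 0%.
4. State whether asymptomatic graded laboratory values enter the table, reconciling Section 11.1.1 with Appendix G, Section 4.0.
5. Reconcile the Cycle 1 Day 1 ECG in Section 5.1.2 with Calendar A.

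The cost is SAP wording and one extra table; no visit or test is added. The downside is that from Cycle 2 a Day 1 draw comes about 14 days after the last scheduled infusion (Day 15 to Day 29), so the supplementary table misses ganetespib effects that recover sooner. It must sit beside the full Arm B table and cannot replace it.
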